2015 (Phase 1) through this NHLS CDW system, we know that approx. 50,000 persons with a CD4<100 were CRAG tested, and 3% (n=1271) have been identified as new CRAG-positive. In Phase 1, approximately 840 persons were CRAG screened per month, and 30 to 35 were found to be CRAG+. Unfortunately, since September 2012, only 63% of CRAG+ persons have been treated with fluconazole, reflecting further training is necessary. In 2016, a live CRAG dashboard was developed by NICD to monitor the national CRAG programme by reporting the 2 above-mentioned indicators (CRAG prevalence and screening coverage). This dashboard presents data mined directly from the CDW and is integrated in the "all ages" NHLS CD4/ VL dashboard.

NICD-GERMS laboratory-based surveillance for cryptococcal meningitis

Currently nested within the NHLS, the National Institute for Communicable Diseases (NICD) is South Africa's national public health government organization for communicable diseases. NICD runs the GERMS-SA surveillance programme. This comprises of a nationwide network of approx. 200 clinical microbiology laboratories (in the public and private sector) which report cases through the NICD/GERMS-SA active lab-based surveillance programme for a number of diseases of public health importance, including cryptococcal meningitis since 2005. The denominator for this surveillance is assumed to be the entire population of SA (approximately 53 million people). In recent years, NICD has obtained surveillance data for the public sector from NHLS CDW. Additionally, at 25 hospitals in all 9 provinces, NICD has employed nurses to collect additional clinical and epidemiological information on lab-confirmed cases of cryptococcosis (from 2014 onwards, for only 3 months a year).

In addition, there are several other surveillance systems that could be used to monitor the cascade of care among those screened for CRAG with advanced HIV disease

District Health Information System (national)

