- 3) Integration with WHO universal HIV test-and-treat guidelines: South Africa adopted the WHO universal HIV test-and-treat guidelines in September 2016. While the National Department of Health has indicated that a baseline CD4 count should be ordered for all patients starting ART, in practice many patients are initiated on ART on the same day as HIV diagnosis, well before the baseline CD4 and reflex CrAg results are available. In KwaZulu-Natal, the provincial department has recently recommended routine same-day ART initiation at all its facilities.

It is unknown if same-day ART initiation among those with advanced HIV would have an adverse impact on patient outcomes at a programmatic level (as a result of unmasking IRIS). Conversely, even reflex CRAG screening may potentially delay ART initiation for those who ultimately screen CRAG negative but should be fast tracked onto ART to reduce risk of HIV progression and other OIs. We have previously described shorter median times to ART initiation amongst those CRAG-screened compared to those not screened (32).

- 4) Impact of training: We have previously implemented training workshops for health care providers (doctors, nurses, pharmacists, counsellors) with the goal of improving clinical management of cryptococcal disease. However the impact of these workshops on patient outcomes has not been measured.
- 5) Optimal treatment regimen for asymptomatic CRAG+ persons. Although CRAG+ persons receiving fluconazole generally do better than if not treated at all, 25%-30% go on to develop meningitis or die despite the WHO-recommended antifungal therapy and ART. A 2.9-fold worse survival was observed in asymptomatic CRAG+ vs. CRAG- persons with CD4 count <200 cells/µL in Tanzania and Zambia (33) (Figure 7).

The current WHO regimen for asymptomatic CRAG+ patients was based on expert opinion and extrapolated from management of symptomatic cryptococcal meningitis.

This regimen likely requires further refinement. As an example, preliminary results from the ORCAS trial in Uganda suggest that persons with CRAG titres \geq 160 and CD4 count <50 cells/µL are more likely to develop subsequent cryptococcal meningitis compared with those with a lower CRAG titre/ higher CD4 count when receiving current WHO-recommended antifungal therapy. Customized or more intensive therapy for those with high titres may be a useful strategy to reduce CRAG+ mortality (**Figure 8**).

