3 STUDY DESIGN

This is an evaluation of an ongoing national screening programme. In years 1 and 2, we will implement an enhanced metrics and evaluation project at selected sites in all provinces across South Africa to measure 6-month outcomes of this programme, along with operational challenges. In years 2 to 5 we will implement programmatic strategies to maximize 6-month cryptococcal meningitis-free survival.

Per South African standard of care, those with a CD4<100 cells/µL will reflexively get a CRAG test performed on remaining blood specimen. We expect the majority of these persons to be asymptomatic outpatients presenting for routine HIV care, though a small proportion will be persons who present to care because they feel unwell. All participants will receive standard of care treatment for asymptomatic cryptococcal antigenaemia, per South African HIV guidelines.

Primary Objective (years 1 and 2): To implement enhanced surveillance at selected sites to determine the outcomes (overall and for pre-specified subgroups) of a national reflex laboratory CRAG screening and pre-emptive treatment programme in South Africa. We estimate performing enhanced surveillance at **approximately 400 clinics out of 4500 clinics nationally**. A list of surveillance facilities will be agreed upon in discussion with provincial departments of health.

We will assess the cascade of care from CD4 testing to CRAG testing, to receipt of CRAG results by healthcare provider, assessment for symptoms, lumbar puncture if indicated, preemptive treatment for those asymptomatic, and 6-month outcomes.

The initial surveillance performed in Objective 1 will establish **baseline 6-month CRAG+ outcomes** (Year 1 and 2) from which subsequent programmatic interventions will seek to improve.

Subgroup Analyses

A number of subgroup analyses will be performed to understand optimal CRAG screening and treatment programmes. For example, we will compare outcomes amongst CRAG+ persons who:

- a) initiated on ART before CD4/ CRAG results are known (same-day ART initiation in the context of universal HIV test-and-treat) to those who have ART delayed until a minimum of 2 weeks of antifungal treatment completion
- b) rural clinics vs. urban centres
- c) high titres (\geq 160) vs. low titres (<160)

- d) clinics that routinely perform lumbar punctures to those that are unable to perform lumbar punctures (stratified by titre)

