- e) development of culture-positive cryptococcal meningitis. These lab results will be captured by the NHLS database, and additional queries by NICD personnel of medical records of CSF CRAG+ persons will be performed for secondary data review and quality assurance on the rate of capture of meningitis episodes. The GERMS surveillance system run by NICD will continue to capture cryptococcal meningitis among those lost to follow up or who transfer care.
- f) Cryptococcal meningitis-free survival of those who receive secondary prophylaxis vs. none
- g) Special populations: pregnant women, those with liver disease.

Such information will be particularly nuanced to the South African CRAG screening and treatment programme, but will also be informative to other sites in sub Saharan Africa that are initiating similar national programmes.

Active enhanced surveillance

Data will be collected by two methods:

A) primary (retrospective) data collection by chart/ record review at facility level by partners and B) secondary analysis and triangulation of existing laboratory and surveillance datasets.

Primary data collection by partners

We will collaborate with partners in South Africa to conduct active surveillance of all CRAG+ persons at selected facilities using a standardized data collection tool (attached – version 1.0, 4 January 2017). Please see appendix for list of partners, and potential roles. Partners may assist with monitoring and evaluation, capturing health information, contact tracing of those who are lost-to-follow up, and/or collecting operational information.

Partners will review patient demographics and outcomes of those who are CRAG+ by retrospective chart/ record review. This will be performed approximately 3 times over a 6-month period, to obtain information about CRAG result, CD4 result, presence of CNS symptoms, receipt of fluconazole if appropriate, and triage to lumbar puncture if symptomatic, along with timing of ART initiation, 6-month survival, retention-in-care, and incidence of cryptococcal meningitis.

Surveillance will not occur at all facilities across South Africa, but at selected facilities within each South African province. A list of surveillance facilities will be agreed upon in discussion with provincial departments of health.

Secondary analysis and triangulation of existing datasets noted on pages 13 and 14.

- Cohort of those with advanced HIV (CD4 <100), incl. CRAG results
 - Subset of those with a positive CRAG result

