Secondary Objectives:

1. Evaluate cost-effectiveness of real-world CRAG screening and pre-emptive treatment programmes in South Africa.

Cost-effectiveness of CRAG screening and pre-emptive treatment has been evaluated in South Africa using mathematical modelling. However, real-world costs and implementation have not been accounted for. For example, this prior model did not account for the repeated training sessions required for healthcare workers. Theoretical models typically don't account for challenges that are seen on the ground, such as fluconazole stock outs, point-of-care CD4 testing, and variable performance and acceptance of lumbar punctures. Effectiveness will be obtained from Objective 1. Analysis will be from the perspective of the health care payer. We will map out the flow of CRAG screen and treat through the HIV cascade of care.

Costs will be collected on health care workers' salaries and percent effort dedicated to CRAG screening, training, lab testing, transport of lab results, fluconazole, and further evaluation of symptomatic patients such as lumbar puncture will be incorporated. Cost of hospitalization and treatment of cryptococcal meningitis will be an important consideration, and will likely vary depending on hospital site. Cost-outcome measures will include annual cost per patient, cost per death prevented, cost of meningitis-free survival, and cost per quality-adjusted life year gained. Cost effectiveness ratios will be stratified by CRAG titre threshold. Incremental cost-effectiveness ratio (ICER) with interventions from Aim 2 will be compared to Aim 1.

Costs and effectiveness will be stratified by subgroups. For example, we expect variable cost and efficacy amongst:

- a) Rural vs. urban clinics
- b) Clinics where LPs are feasible vs. those that are not
- c) Patients that receive secondary prophylaxis vs. those who stop fluconazole without prophylaxis
- d) High CRAG titre vs. low CRAG titre
- e) Education and Retention-in-care: Efforts for education of patients and healthcare workers, and efforts to improve retention in care such as using SMS will likely be more costly at the clinic level. However, if proven to be efficacious (compared to without these interventions) may be cost-effective interventions.

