4.1 Subject Inclusion Criteria

• Blood CRAG test positive

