8.1 Statistical Analysis Plan

The rate (with 95% confidence interval) for the primary and secondary events will be estimated overall and for pre-specified subgroups during the first 2 years of the study. Those rates will subsequently be compared with the rates after programmatic changes have been made (during years 2-5) to increase the effectiveness of the national screening program.

For the subgroups we will also use time-to-event methods to compare the primary and selected secondary endpoints. The table below reports detectable hazard ratios for the primary event with 80% and 90% power, assuming a two-sided alpha=0.05, 70% CM-free survival in the control group, and the stated number of subgroup participants. For example, if CSF CRAG titre data are available for 1200 participants (with 300 having a titre \geq 160), then we can detect a hazard ratio as small as 1.37, for an almost 10% difference in event-free survival.

Detectable Hazard Ratios for Subgroups					
(Assuming two-sided α =0.05 and 70% event-free survival in the control group)					
		80% Power		90% Power	
	N per		Proportion		Proportion
Subgroup	group	HR	Surviving	HR	Surviving
High CSF CRAG titre	300	1.37	0.61	1.44	0.60
(≥1:160)					
Control	900				
(CSF CRAG titre < 1:160)					

The a priori subgroups of interest are:

- High CRAG titres (\geq 1:160) vs. low titres (<1:160)
- Male vs. Female
- Pregnant vs. Non-pregnant
- Liver Disease (ALT>3x Upper Limit of Normal) vs. No liver disease

- Geographic Location (urban vs. rural)
- Timing of ART Initiation
 - On pre-existing ART
 - Initiated on ART before CD4/ CRAG results are known (same-day ART initiation in the context of universal HIV test-and-treat)
 - ART initiated at 2 weeks
 - ART initiated at >=4 weeks
- Clinic-level outcomes (i.e. cluster) based on proportion of CRAG+ persons receiving Lumbar Punctures.
- Duration of fluconazole use
- Fluconazole secondary prophylaxis vs. none

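### Secondary prophylaxis is compared with an undefined *none* in Section 8.1 and Section 3, but with fluconazole stoppers in the cost-effectiveness objective; read literally, *none* would favour prophylaxis

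*Protocol*

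**What the plan says.** The contrast appears in three places in the protocol.

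- Section 8.1, a priori subgroups: "Fluconazole secondary prophylaxis vs. none".
- Section 3, Subgroup Analyses, item (f): "Cryptococcal meningitis-free survival of those who receive secondary prophylaxis vs. none".
- Section 3, Secondary Objectives, cost-effectiveness, item (c): "Patients that receive secondary prophylaxis vs. those who stop fluconazole without prophylaxis".

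The first two do not say who belongs to *none*. The third does: its comparator must have started fluconazole in order to stop it.

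The population for the subgroup work is broad. Section 3 introduces the list with "we will compare outcomes amongst CRAG+ persons who", and the only inclusion criterion in Section 4.1 is "Blood CRAG test positive" (Section 4.2 excludes those under 18). Receipt of fluconazole is not required.

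Two background statements in Section 1.1 bear on the consequence. In Phase 1, "only 63% of CRAG+ persons have been treated with fluconazole". On outcome, "Although CRAG+ persons receiving fluconazole generally do better than if not treated at all, 25%-30% go on to develop meningitis or die" despite the recommended therapy.

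**The concern.** Secondary prophylaxis follows earlier treatment, so the useful question is what continuing fluconazole adds for patients who have already taken it. The cost-effectiveness item asks that question. The other two, taken at their words, compare prophylaxis recipients with everyone else in a CRAG-positive cohort. That adds two kinds of patient to the comparator:

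1. patients who never received fluconazole, for whom continuing it was never at issue;
2. patients who died or developed meningitis before prophylaxis could have started.

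Both would tend to lower event-free survival in *none*. The difference would then mix the value of continuing fluconazole with the value of having had any, and with the fact that recipients had to survive to the start of prophylaxis. A reader could take the whole difference as the benefit of prophylaxis.

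**Working it through.** The protocol gives no sample size, power or effect for this contrast, so there is no figure to reproduce. Its only power table concerns CRAG titre. The steps below are illustrations of direction and possible size, each assuming prophylaxis has no true effect.

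**Inputs**

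- Treated in Phase 1: 63% (Section 1.1), so never treated 100% − 63% = 37%.
- Event-free survival if treated, S_T: 70% to 75%, from the 25%–30% failure figure in Section 1.1; Section 8.1 also uses 70% for its control group.
- Prophylaxis uptake among treated patients, q: not given; assumed 25%, 50%, 75%.
- Event-free survival if never treated, S_U: not given; assumed 40% to 70%.

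**Step 1. Never-treated share of *none*, read literally**

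Share = 0.37 / [0.37 + 0.63 × (1 − q)]

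- q = 0.25: 0.37 / 0.8425 = 44%
- q = 0.50: 0.37 / 0.685 = 54%
- q = 0.75: 0.37 / 0.5275 = 70%

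**Step 2. Spurious difference from that mixture**

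Difference = share × (S_T − S_U). With S_T = 70%, in percentage points:

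| S_U | q = 0.25 | q = 0.50 | q = 0.75 |
|---|---|---|---|
| 70% | 0 | 0 | 0 |
| 60% | 4.4 | 5.4 | 7.0 |
| 50% | 8.8 | 10.8 | 14.0 |
| 40% | 13.2 | 16.2 | 21.0 |

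With S_T = 75%, the largest value on the grid is 24.5 points (S_U = 40%, q = 0.75). The range is therefore 0 to about 25 points.

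**Step 3. Early failures, among fluconazole starters only**

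The protocol does not define when secondary prophylaxis begins. Assume it is the last phase of the regimen described in Section 1.1, which follows phases of 2 and 8 weeks, so week 10 of 26. Assume a constant hazard, and let q now be the share of those event-free at week 10 who receive prophylaxis. With S_T = 70% and q = 0.50:

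- event-free at week 10: 0.70^(10/26) = 0.872
- recipients, event-free at 6 months: 0.70 / 0.872 = 80.3%
- all other starters: (0.70 − 0.5 × 0.70) / (1 − 0.5 × 0.872) = 62.0%

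That is a gap of about 18 points with no effect. Over S_T of 70%–75% and q of 25%–75% it runs from about 11 to 30 points.

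**Step 4. Is a landmark alone enough?**

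Take S_T = 70%, S_U = 50%, q = 0.50 and a week-10 landmark applied to the whole cohort. Never-treated patients event-free at week 10: 0.50^(10/26) = 0.766. Their share of *none* is 0.37 × 0.766 / (0.37 × 0.766 + 0.63 × 0.5 × 0.872) = 51%. Their later survival is 0.50 / 0.766 = 65.3%, so the residual bias is 0.508 × (80.3 − 65.3) = 7.6 points. Restriction to starters and handling of time are both needed; neither replaces the other.

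**The case against.** The strongest reply is that Section 8.1 is a list of short labels. Secondary prophylaxis ordinarily presupposes prior treatment, so *none* may be shorthand for the fuller wording in the cost-effectiveness item, and an analysis plan not shown here may say so. This stands in part. No passage says that *none* includes never-treated patients, and none excludes them. A reader might infer that the protocol does include them and does overstate the benefit. The documents support only the conditional: if they are included, the contrast favours prophylaxis. Even so, the protocol words one comparison in two ways, and the wider wording matches its stated population.

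A reader might also infer, from "Effectiveness will be obtained from Objective 1", that the cost-effectiveness result would join costs from one comparator to effects from another. That is not supported. The same part of Section 3 says that costs and effectiveness are both stratified by its own subgroup list, which contains the stoppers comparator. Objective 1 supplies the outcome data; nothing says the contrast in Section 8.1 is carried across.

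The size is open to challenge too. The 63% describes Phase 1, which Section 8.2 places in four districts, and not the national cohort. Uptake and untreated survival are assumed. These objections stand, and they are why the range starts at zero.

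Finally, adopting the stoppers comparator alone would leave the early-failure problem of Step 3, which could be as large or larger. That is correct, and the fix has to cover it.

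**Conclusion.** The point holds as a definition to be reconciled. Two statements of the outcome contrast use an undefined *none* in a cohort of all CRAG-positive adults; the third uses patients who stop fluconazole. On a literal reading, the wider comparator takes in never-treated patients and early failures. The direction, in favour of prophylaxis, follows for the never-treated from the protocol's own statement that treated patients generally do better, and for early failures from the order of events.

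No size can be claimed for this study. The 44%–70% share rests on the Phase 1 treatment figure and assumed uptake. The 0 to 25 point range rests further on assumed untreated survival. The 11 to 30 points for early failures rest on an assumed week-10 start and a constant hazard, and should not simply be added to the mixture figure. This is one subgroup among several, without a stated power or decision rule, so the matter is worth correcting but does not touch the overall primary estimate.

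**What to change.** In Section 3 item (f) and in Section 8.1, replace *none* with the comparator already used in the cost-effectiveness item, and restrict the contrast to CRAG-positive patients who started fluconazole: those who go on to secondary prophylaxis against those who stop without it. Report never-treated patients as a separate descriptive group.

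State how time is handled. Either treat prophylaxis as a time-dependent exposure, so that time before it starts counts as unexposed, or begin follow-up at a pre-specified landmark among patients alive and meningitis-free. Either way the protocol must say what counts as secondary prophylaxis and when it is taken to begin; that definition is for the sponsor.

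The text change is a line or two in each place. Section 5 already has fluconazole doses, dates and completion abstracted, with survival status and date last known alive, so no new data item is needed for the exposure groups. The price is a smaller comparison group and, with a landmark, a result that applies only to patients who reach it.

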8.2 Sample Size Considerations

Sample size will depend on number of persons CRAG screened under the national CRAG screening program. Within 4 districts in Gauteng and Free State provinces between September 2012 and September 2015 through this NHLS CDW system, we know that 50,000 persons with a CD4<100 have been CrAg tested, and 3% have been identified as CRAG-positive. With national CRAG screening, we expect 6000 to 8000 asymptomatic CRAG+ cases to be detected per year and 15000 to 17000 symptomatic CRAG+ or cryptococcal meningitis cases per year.

Quality Control and Quality Assurance

Data verification will occur in the first 2 years of the study, where we will evaluate a sample of clinic and laboratory records in detail, and describe the baseline rate of error that can be expected from our data.

Ongoing data quality control (QC) and quality assurance (QA) activities will occur via data management system. **Clinical Quality Management Plan** (CQMP) reports will include:

- Summary of Data Completeness
- Case Report Form (CRF) Delinquency Report
- Delinquent CRFs by Participant ID

9 ETHICS/PROTECTION OF HUMAN SUBJECTS

9.1 Ethical Standard

The investigators will ensure that this study is conducted in full conformity with the principles set forth in The Belmont Report: Ethical Principles and Guidelines for the Protection of Human Subjects of Research of the US National Commission for the Protection of Human Subjects of Biomedical and Behavioral Research (April 18, 1979) and codified in 45 CFR Part 46 and/or the ICH E6; 62 Federal Regulations 25691 (1997). This study will be in compliance with the Declaration of Helsinki, CIOMS, International Ethical Guidelines for Biomedical Research Involving Human Subjects (2002).

9.2 Ethics Committee Review

We are retrospectively monitoring an ongoing national screening programme that is considered standard of care in South Africa. Data collection will only be performed retrospectively, thus informed consent will not be obtained for this study.

If further interventions that are beyond the standard of care are pursued, an amendment will be made to this protocol, and further review will be pursued with the local ethics committees.

